**Other endpoints:**

- At LT weeks 104 and 156 neurocognitive evaluation for secondary hypertensive patients only

Patient demographics and relevant baseline characteristics will be obtained from the core study (CSPP100A2365) and summarized by actual treatment regimen at the end of study CSPP100A2365E1 (aliskiren vs. enalapril). Key measurements (weight, height, BMI and neurocognitive assessments), both raw values and their changes from baseline, will be summarized by visit (as recorded in the CRF) and treatment regimen. Safety observations will be summarized by treatment regimen.

Treatment regimen in this document refers to actual treatment regimen at the end of study CSPP100A2365E1 (aliskiren vs. enalapril)

Unless stated otherwise, baseline refers to the core study (CSPP100A2365) baseline.

Unless stated otherwise, statistical tests will be carried out at a two-sided significance level of 0.05 using SAS® statistical software (██████████) version 9.3 or higher.

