##### Categorical variables:

- Age groups (6-11 years, 12-17 years, and 6 – 12 years, 13-17 years)
- Sex (Male, Female)
- Race (Caucasian, Asian, Black, Native American, Pacific Islander and Other)
- Ethnicity (Hispanic/Latino, Chinese, Indian (Indian subcontinent), Japanese, Mixed ethnicity and Other)
- Weight category ( $\geq 20$  kg and  $< 50$ kg,  $\geq 50$  kg and  $< 80$ kg,  $\geq 80$  kg and  $\leq 150$  kg)
- Hypertension etiology (primary, secondary)
- eGFR category ( $< 60$ ,  $\geq 60$  ml/min/SA and  $< 90$ ,  $\geq 90$  ml/min/SA)
- BMI category ( $< 95^{\text{th}}$  percentile and  $\geq 95^{\text{th}}$  percentile)

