##### Continuous variables:

- Age (years), Height (cm), Weight (kg), BMI ( $\text{Kg}/\text{m}^2$ ), eGFR (ml/min/SA)
- msSBP (mmHg), msDBP (mmHg), sitting pulse (bpm), standing systolic/diastolic blood pressure (mmHg)

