#### Primary analysis

The primary analysis will be a superiority assessment of change in weight, height and BMI from baseline to visit LT 18. For the purpose of describing the analysis of primary variables, weight will be used to describe the analysis. Height and BMI will be analysed in exactly the same fashion as described for the weight in this section. The null hypothesis to be tested is that the mean change of weight at visit LT 18, in the aliskiren regimen is equal to that in the enalapril regimen, versus the alternative hypothesis that they are not equal:

H0:  $\mu_1 = \mu_2$  versus H1:  $\mu_1 \neq \mu_2$

Where  $\mu_1$  and  $\mu_2$  are the mean of the change in weight from baseline to visit LT 18, for aliskiren and enalapril, respectively. This hypothesis will be tested at a two-sided significance level of 0.05 using an analysis of covariance (ANCOVA) model with treatment regimen, region (US, Euro), age strata at baseline (6 to 11 years, 12 to 17 years), and hypertension etiology (primary, secondary) as factors, and with baseline weight as the baseline covariate (refer to appendix 1). The estimated change from baseline and the 95% confidence interval for  $\mu_1 - \mu_2$  will be presented. For the analysis of change in height, the baseline height will be included as the baseline covariate in the model. For the analysis of change in BMI, baseline BMI will be included as the baseline covariate in the model. Missing values will not be imputed.

No multiplicity adjustment will be performed.

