### Sensitivity analysis

A sensitivity analysis will be performed by repeating the primary analysis by imputing any missing values of weight/height/BMI at visit LT 18 by LOCF method from visit LT 17. Other missing values in the data will not be imputed.

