### Secondary analysis

The analysis of secondary endpoints will be similar to the primary analysis. The secondary endpoints, changes in weight, height, BMI from baseline to end of study, will be analysed by hypertension group.

The estimated change from baseline and the 95% confidence interval for the difference between treatment groups at end of study will be presented for each hypertension group.

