#### Appendix 1: SAS code for ANCOVA model

```

ods graphics on;
proc mixed data=one;
  class treatment region age etiology;
  model change = treatment region age etiology baseline_covariate /
solution residual;
  estimate 'Aliskiren vs Enalapril' treatment 1 -1/CL;
run;
ods graphics off;

```

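### The primary growth ANCOVA uses age only as two six-year bands and omits sex, so the height interval is probably wider than the collected data require

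*SAP*

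**What the plan says.** SAP 1.2.6.1 states: "The primary analysis will be a superiority assessment of change in weight, height and BMI from baseline to visit LT 18". Weight is written out as the example, and height and BMI follow the same method, each with its own baseline value as covariate. The remaining terms are regimen, region, "age strata at baseline (6 to 11 years, 12 to 17 years), and hypertension etiology (primary, secondary) as factors, and with baseline weight". SAP Appendix 1 confirms this: "model change = treatment region age etiology baseline_covariate", with age declared as a class variable and no sex term. Protocol 9.4.2 has the same terms.

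The other growth analyses add no covariates:
- The only sensitivity analysis repeats the primary model after "imputing any missing values of weight/height/BMI at visit LT 18 by LOCF method from visit LT 17".
- For the by-etiology endpoints, "The analysis of secondary endpoints will be similar to the primary analysis".
- Protocol 9.4.4 plans no supportive analyses.

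Sex and age in years are recorded at core baseline. Both appear in the SAP 1.2.4 tables and listings (the continuous list reads "Age (years), Height (cm), Weight (kg), BMI" and continues), but in no growth model.

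**The concern.** The outcome is raw change in cm, kg or kg/m² over roughly two years in children who were 6–17 at core baseline. Protocol 1.1 expects half or more to be 6–11, with pre-pubertal children included, so the sample should span puberty. Expected height gain then differs sharply by age and sex within each band: a 12-year-old and a 17-year-old share one level of the age factor, and boys and girls are not separated. Baseline height stands in for age only partly. What remains goes into the residual variance and widens the confidence interval.

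Height is one of the SAP's primary analyses, and growth is the study's only objective. The sample size is whatever number of E1 completers enrol (protocol 9.6, SAP 1.3), so lost precision cannot be recovered by recruiting more patients.

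**Working it through.** The plan gives no sample size, SD, effect size or power, so it has no figure of its own to reproduce. All growth inputs below are assumptions.

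**Follow-up.** Core study 8 weeks (protocol 1.1) plus LT week 104 gives 112 weeks, and 112/52 = 2.15 years.

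**Formula.** With the design otherwise unchanged, interval width is proportional to residual SD. If VR is the residual variance of the planned model divided by that of the extended model, large-sample narrowing = 1 − 1/√VR. The extended model adds sex, age, age², sex×age and sex×age².

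**Assumed inputs.**
- Run A: 100,000 children, half aged 6–11, uniform age within band, sexes equal; 5.5 cm/yr before puberty plus a 3 cm/yr spurt, boys 1–2 years later than girls; timing SD 0.7–1.2 years; extra SD 1–2 cm.
- Run B: 144 scenarios of 60,000 children, half aged 6–11, 55% male, 40% secondary hypertension; 5–5.5 cm/yr with a typical or flatter spurt at about 12 (girls) and 13.5 (boys). Varied: timing SD (0.7, 1.3 years), other height-change SD (1, 2.5, 4 cm), BMI-change SD (1.5, 2.5, 3.5), two BMI trends, and etiology effect (none, or 15% slower height gain in secondary).
- Runs C and D: further spurt curves, with the share aged 6–11 varied.

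**Validity.** Under random allocation with no drug effect, type I error of the planned height model at 100 per arm was 0.050, 0.055 and 0.053 in run A (1,500 replicates; Monte Carlo SE √(0.05×0.95/1500) = 0.006). In run B it was 4.9–5.2%. The planned test holds its level.

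**Height, extended model.**

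| Run | Share aged 6–11 | VR | Narrowing |
|---|---|---|---|
| A | 50% | 1/0.74 to 1/0.50 = 1.35–2.00 | 14–29% |
| B | 50% | 1.27–2.29 | 11–34% |
| C | 50% | – | 12–29% |
| D | 50% | 1.24–1.83 | 10–26% |
| C | 65% | – | 10–26% |
| C | 80% | – | 7–21% |
| D | 80% | 1.12–1.50 | 5–18% |

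Example (run A, middle case): residual SD falls from 4.25 to 3.24 cm, and 1 − 3.24/4.25 = 24%.

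**Which terms matter.** In run A, sex alone gives variance ratios (extended/planned) of 0.99, 0.94 and 0.93, or 0.5–4% narrower. Sex plus linear age gives 0.88, 0.82 and 0.80, or 6–11% narrower. Run B gives VR 1.05–1.20 for sex plus linear age (2–9%), and run C gives 0–1% at an 80% share. Most of the gain therefore needs the curved age terms.

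**Weight.** Run A: 0.95–0.97, so 1.5–2.5% narrower. Run D: VR 1.05–1.13, so 2–6%. Run B: 1.06–1.51, so 3–19%. The top of run B is well above the other two runs.

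**BMI.** Run A: no change. Run B: VR 1.00–1.08.

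**Finite samples (run B, half aged 6–11).**

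| N | Height | Weight | BMI |
|---|---|---|---|
| 200 | 10–33% narrower (median 19%) | 1–17% narrower (median 6%) | 2% narrower to 2% wider |
| 60 | 6–30% narrower | 14% narrower to 3% wider | 1–6% wider |

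At N=200 the median height half-width falls from 1.36 to 1.09 cm.

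**If balance failed (hypothetical; run B curves, 12–17 band).** A 0.5-year gap in mean age would shift the planned height estimate by 0.42–0.59 cm. A 10-point gap in the share of males would shift it by 0.18–0.25 cm. At N=200 these are 0.26–0.47 and 0.09–0.20 of the planned half-width.

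**The case against.** The strongest reply is that nothing is wrong. The model is a conventional pre-specified ANCOVA on design strata plus the baseline value, it holds its type I error, and the documents set no precision target that a wider interval could miss. That stands against any claim of invalidity. It does not remove a gain available from data already collected.

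Three further objections limit the size, and all stand. Fixing the 6–11 share at one half takes the bottom of the protocol's stated range and gives the largest gains. The benefit falls on one of three growth outcomes. Most of it depends on curvature in age, for which the documents hold no growth data.

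On timing, the SAP describes follow-up in the past tense, protocol 5.4 provides no blinding, and the documents do not say whether regimen-level data have been seen. Replacing a valid primary model after such data were seen could look data-driven.

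A reader might go further and infer that the treatment comparison is biased, because the analysis set is re-consented completers and "Treatment regimen in this document refers to actual treatment regimen at the end of study CSPP100A2365E1". The documents do not support that. Chance imbalance is already covered by the planned standard error. Only selective imbalance would bias the estimate, no section indicates one, and the baseline tables by regimen would show it.

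**Conclusion.** The point holds as a loss of precision, mainly for height, in a model that is valid under balance. On assumed growth curves, the large-sample height interval could be about 10–34% narrower if half the children are aged 6–11, and about 5–21% narrower if 80% are. Sex plus linear age alone would recover about 0–11%. Weight would probably gain about 1.5–6%, reaching 19% only under the widest assumptions. BMI is unchanged, or slightly wider in small samples. The direction for height was the same in every run; the sizes are illustrative. Bias from age or sex imbalance remains hypothetical. This is a cheap improvement.

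**What to change.** Keep every existing term. For height at LT 18, add sex to the CLASS statement of SAP Appendix 1 and append `sex agey agey*agey sex*agey sex*agey*agey` to the model line, with agey = age in years at core baseline, centred at 12. Use the same terms for weight and BMI only if one common model is wanted.

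- **If regimen-level data have not been reviewed:** make this the primary model, fix it before that review, and amend protocol 9.4.2 to match. SAP 2.0.0 itself revised the primary analysis, so this route has a precedent.
- **Otherwise:** add it beside LOCF as a covariate-adjusted sensitivity analysis for height, without imputation, reported as an estimate with a 95% CI and not as a further test. This leaves the primary interval unchanged. State in the SAP when it was added relative to data review.

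State that the terms do not carry over by default to the by-etiology analyses. In a single group of 30, run B curves gave height from 29% narrower to 3% wider, weight from 13% narrower to 12% wider, and BMI 4–15% wider.

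Cost: no new data, one CLASS entry and one model line, one SAP sentence, and a protocol amendment if it becomes primary. It uses five degrees of freedom; if applied to BMI, that interval is about 1% wider at N=200 and about 5% wider at N=60 (medians).

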3.1 Study design

This is a multicenter 52 to 104 week off-therapy extension to evaluate long-term growth and development in pediatric hypertensive patients 6 – 17 years of age at initiation of treatment with aliskiren in study CSPP100A2365. Eligible patients will continue to be stratified by age (6 – 11 years and 12 – 17 years) at study CSPP100A2365 baseline (Visit 2) and by etiology of hypertension (primary and secondary). Likewise, stratifications by weight group and region assigned in study CSPP100A2365 will remain.

Table 3-1 Study design

[figure not shown]
CSPP100A2365E2 LT Safety Follow-up		
Week 52 LT (end of study visit CSPP100A2365E1)	Week 104 LT	Week 156 LT
Day 365 (LT)	Day 730 (LT)	Day1095 (LT)
Visit 17*	Visit 18**	Visit 19***

* Long-term (LT) safety extension visit numbers continue from CSPP100A2365E1

** End of study for patients with primary hypertension

*** End of study for patients with secondary hypertension

Figure 3-1 Study design

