### **1.2 Statistical and analytical plans**

The purpose of this 52 to 104 week off-therapy follow-up to studies CSPP100A2365 and CSPP100A2365E1 is to evaluate the long-term growth and development of children 6 – 17 years old (6 to less than 18 years old at baseline in study CSPP100A2365) with hypertension (msSBP  $\geq$  95th percentile for age, gender and height) at baseline in study CSPP100A2365, previously treated with aliskiren. Patients identified in study CSPP100A2365 to have primary hypertension were followed for 52 weeks (1 year) after the completion of study CSPP100A2365E1 (aliskiren vs. enalapril). Patients identified in study CSPP100A2365 to have secondary hypertension were followed for 104 weeks (2 years) after the completion of study CSPP100A2365E1. The assessment of growth and development through height and weight measurement was performed on all patients for 52 weeks, after which patients with primary hypertension completed the study. The assessment of patients with secondary hypertension continued for an additional 52 weeks during which growth and development was continually assessed with added neurocognitive and renal function evaluations.

The study population consists of male and female hypertensive pediatric patients who have completed study CSPP100A2365E1. These patients were 6 – 17 years old and had an msSBP  $\geq$  95th percentile for age, gender and height at baseline (randomization) in study CSPP100A2365. Patients will continue to be stratified by CSPP100A2365 baseline weight at Visit 2, baseline age group, hypertension etiology (primary or secondary) and region. Centers (approximately 70) from the US, EU and ROW participating in CSPP100A2365 and CSPP100A2365E1 will participate in this off-therapy follow-up.

The follow up visits 52 and 104 weeks of the study follow up will be referred to as Week 104 and Week 156, respectively, in the CSPP100A2365E2 study documents and output.

The primary objective of the study is

- To evaluate the long term growth and development of pediatric hypertensive patients 6 – 17 years of age when previously treated with aliskiren.

This objective will be evaluated by assessing the following endpoints:

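### The height and BMI ANCOVAs contain no weight term, although baseline weight group is named as a retained stratification factor; adding one is a cheap improvement of unknown size

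*SAP*

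**What the plan says.** SAP 1.2 lists the factors that are kept: "Patients will continue to be stratified by CSPP100A2365 baseline weight at Visit 2, baseline age group, hypertension etiology (primary or secondary) and region". Protocol 3.1 agrees: "Likewise, stratifications by weight group and region assigned in study CSPP100A2365 will remain". The protocol synopsis and Section 4 name the same four factors.

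The primary analysis in SAP 1.2.6.1 fits change from baseline to visit LT 18 on treatment regimen, with "region (US, Euro), age strata at baseline (6 to 11 years, 12 to 17 years), and hypertension etiology (primary, secondary) as factors", plus one baseline covariate. That covariate is baseline weight in the weight model. For the other two endpoints it is replaced: "For the analysis of change in height, the baseline height will be included as the baseline covariate in the model" and "For the analysis of change in BMI, baseline BMI will be included as the baseline covariate in the model". The Appendix 1 code matches, with a single covariate slot: "model change = treatment region age etiology baseline_covariate".

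Protocol 9.4.2 names baseline weight as covariate for the weight analysis and says only that height and BMI are handled by a similar model. SAP 1.2.4 lists a three-level "Weight category" variable (20 to under 50, 50 to under 80, and 80 to 150 kg) among the baseline characteristics. It does not say that these are the core-study strata.

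**The concern.** The plan models three of its four retained strata in every growth analysis and the fourth in only one, without comment. Height and BMI change are primary endpoints, and growth is part of the study's only objective. The gap also carries into the LOCF sensitivity run, which repeats the primary model, and into the by-hypertension-group analyses, which are described as similar to it.

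What is at stake depends on whether weight group is prognostic for growth once region, age stratum, etiology and the endpoint's own baseline are in the model. That is plausible for height. The age strata are six-year bands in growing children, weights run from 20 to 150 kg, and Protocol 1.1 itself links pediatric hypertension to obesity. If weight group is prognostic, there are two cases:

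- Regimens balanced on weight group: its variance stays in the residual and precision is given up.
- Regimens not balanced on it: part of the weight-group effect is carried into the treatment estimate.

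The second case cannot be dismissed. SAP 1.2 defines the contrast by the regimen actually taken at the end of the first extension (E1), and the analysis set is E1 completers who signed consent for follow-up.

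**Working it through.** **1. Which terms are in which model (SAP 1.2.6.1 and Appendix 1)**

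| Retained stratum | Weight model | Height model | BMI model |
|---|---|---|---|
| Region | factor | factor | factor |
| Age group | factor | factor | factor |
| Etiology | factor | factor | factor |
| Weight group | continuous baseline weight | absent | absent |

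**2. Inputs.** The documents give no sample size, SD, effect size, power or interval width, so there is no stated figure to reproduce. Two quantities are assumed: N from 50 to 300, and a partial R² from 0 to 0.20. The partial R² is the share of residual variance in height or BMI change that weight group explains after the other model terms.

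**3. Formula.** The planned model has 6 parameters (intercept, treatment, region, age, etiology, baseline), which leaves N−6 residual degrees of freedom. A three-level weight group adds 2, which leaves N−8. The ratio of interval width with weight group to width without is:

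- Regimens balanced on weight group: √(1−R²) × t(0.975, N−8) / t(0.975, N−6).
- Chance imbalance: the same, multiplied by √((N−7)/(N−9)), an approximate allowance for the added variance of the treatment estimate.

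Example, N = 50 and R² = 0: t(42)/t(44) = 2.0181/2.0154 = 1.0013. Multiplied by √(43/41) = 1.0241, this gives 1.0255, about 2.6% wider.

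Example, N = 100 and R² = 0.20, balanced: √0.80 × 1.9861/1.9855 = 0.8947, about 10.5% narrower.

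**4. Results (width ratio, balanced / chance imbalance)**

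| Partial R² | N = 50 | N = 100 | N = 200 | N = 300 |
|---|---|---|---|---|
| 0 | 1.001 / 1.026 | 1.000 / 1.011 | 1.000 / 1.005 | 1.000 / 1.004 |
| 0.02 | 0.991 / 1.015 | 0.990 / 1.001 | 0.990 / 0.995 | 0.990 / 0.993 |
| 0.05 | 0.976 / 1.000 | 0.975 / 0.986 | 0.975 / 0.980 | 0.975 / 0.978 |
| 0.10 | 0.950 / 0.973 | 0.949 / 0.959 | 0.949 / 0.954 | 0.949 / 0.952 |
| 0.20 | 0.896 / 0.917 | 0.895 / 0.905 | 0.895 / 0.899 | 0.895 / 0.898 |

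With chance imbalance, the break-even partial R² is about 0.049 at N = 50, 0.022 at N = 100, 0.011 at N = 200 and 0.007 at N = 300. Below it, adding weight group widens the interval slightly.

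**5. Continuous weight instead.** One added parameter gives √(1−R²) × t(0.975, N−7)/t(0.975, N−6), multiplied by √((N−7)/(N−8)) for chance imbalance. At N = 50 and R² = 0 this is 1.0007 × √(43/42) = 1.0125. The worst-case widening is about half that of the three-level factor.

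**6. Height versus BMI.** An illustrative simulation assumed ages uniform from 6 to 18, height and BMI rising with age, a BMI SD of 5 or 7 kg/m², and weight limited to 20 to 150 kg. Age stratum plus baseline height explained 51% to 67% of the variance in log weight. Age stratum plus baseline BMI explained 84% to 86%. The BMI model therefore already holds most of the weight information, and the height model less. These figures show overlap between baseline variables only. They do not show how well weight predicts growth.

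**The case against.** The strongest case against is that no loss has been shown. This is an off-therapy safety follow-up with no power target, and the SAP keeps the factors of the protocol's own model. Baseline height or BMI together with age stratum already carries part of the weight information. In a small sample a non-prognostic term costs a little precision. All of that stands, and it is why the size is left open.

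A reader might infer more than the documents support:

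- **That the planned intervals are wider than they need to be.** This requires a partial R² above the break-even value, and nothing in the documents gives one. A gain of a few per cent can be produced by simulating assumed growth curves, but the curves then decide the answer. Part of that gain would reflect age within the wide age bands.
- **That the tests run below 5%.** With full balance, 2·P(Z > 1.96/√(1−R²)) gives 0.048, 0.044 and 0.039 at R² = 0.02, 0.05 and 0.10. That balance is not documented. The strata were assigned in the core study, the contrast is the actual E1 regimen, and no section says E1 allocation was balanced within weight group. This extension assigns no treatment, so the retained strata are labels carried forward.
- **That the weight categories in SAP 1.2.4 are the missing stratum.** They are listed only as a baseline characteristic.

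The doubt about balance does not remove the case for a weight term. It moves the reason from precision towards protection against bias.

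**Conclusion.** The omission is certain: weight group is called a retained stratification factor, is absent from the height and BMI models, and no reason is given. Its consequence is conditional. If weight group is prognostic after the other terms, the comparison loses precision under balance and may be biased under imbalance.

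The size cannot be found from the documents. Under the assumptions above, interval width would change by between about +2.6% and about −10.5%. At a partial R² of 0.05 or less the narrowing is at most about 2.5%. No separate gain has been shown for BMI, where it is probably smaller than for height. No conclusion of the study is shown to change. This is a low-cost improvement, not a flaw that undermines the analysis.

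**What to change.** In SAP 1.2.6.1 and Appendix 1, add baseline weight to the height and BMI models in one of two forms:

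- the core-study weight stratum as a CLASS factor, using the three-level category in SAP 1.2.4 if it is confirmed to be that stratum; or
- continuous core-study baseline weight, as a second covariate.

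Choose the form before the data are analysed. Apply it in the primary and LOCF runs, and in the by-hypertension-group runs where numbers allow, since each of those has fewer patients. Leave the weight model unchanged. If the sponsor prefers the present models, the SAP should say why weight group is left out and prespecify a sensitivity analysis that includes it.

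The cost is one model term, a sentence in the SAP, and one degree of freedom (continuous) or two (three-level). Baseline weight is already collected in the core study, before treatment. The downside is a slight widening if the sample is small and weight is not prognostic: at N = 50, about 1.3% for continuous weight and 2.6% for the three-level factor.

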5.5.12 Early study termination

The study can be terminated at any time for any reason by Novartis. Should this be necessary, the patient should be seen as soon as possible and treated as described in Section 6 for a prematurely withdrawn patient. The investigator may be informed of additional procedures to be followed in order to ensure that adequate consideration is given to the protection of the patient's interests. The investigator will be responsible for informing IRBs and/or ECs of the early termination of the trial.

6 Visit schedule and assessments

Table 6-1 Assessment schedule

Visit	C ⁴	LT17 ¹	LT18	LT19 ³
Week		52	104	156
Informed consent/child assent	S	X		
Height	D	X	X	X
Weight	D	X	X	X
Concomitant Medication	D	X	X	X
Neurocognitive Evaluation	D		X ³	X
Chemistry	D		X ³	X
Study Completion Form	D		X ²	X

¹ Extension 2 – Visit LT (long term) 17 should occur on the same day as CSPP100A2365E1 “end of study” V16. Data for other identified evaluations will be obtained from Study CSPP100A2365E1.

² Visit LT18 is the end of study visit for patients identified in the core study (CSPP100A2365) as having primary hypertension.

³ For patients with secondary hypertension only.

⁴ C is the category; D = eCRF data, S = source document data

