9.4.3 Handling of missing values/censoring/discontinuations

Not planned.

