**1.2.1 Population of analysis**

The **Enrolled to Follow-up Set (EFS)** will consist of all patients who sign the informed consent form for CSPP100A2365E2. Patients will be analyzed according to the treatment received in the CSPP100A2365E1 study.

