#### **1.2.6 Analysis of primary variables**

The primary endpoints are the changes in weight, height, BMI and neurocognitive assessments from baseline to visit LT 18 for the EFS.

Baseline is defined as the baseline observation taken from the core CSPP100A2365 study. The changes from baseline in primary endpoints will be calculated as value at visit LT 18 – value at Baseline.

End of CSPP100A2365E2 study is visit LT 18 for the primary hypertension group and visit LT 19 for the secondary hypertension group. Visit LT 17 is end of study visit from CSPP100A2365E1 study.

The secondary endpoints are the changes in weight, height, BMI and neurocognitive assessments from baseline to end of study, by hypertension group.

The changes from baseline in secondary endpoints will be calculated as (value at the End of Study visit) – (value at Baseline).

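### The primary growth ANCOVA uses only patients with an LT 18 value and ignores LT 17, which costs precision and can bias the regimen difference if growth-related loss operates unequally by regimen

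*SAP*

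**What the plan says.** SAP 1.2.6 sets the primary endpoints as changes "from baseline to visit LT 18 for the EFS". Under SAP 1.2.1 the EFS "will consist of all patients who sign the informed consent form for CSPP100A2365E2". The derivation is given as: "The changes from baseline in primary endpoints will be calculated as value at visit LT 18 – value at Baseline".

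For the comparison of regimens, the Primary analysis part of SAP 1.2.6.1 says: "This hypothesis will be tested at a two-sided significance level of 0.05 using an analysis of covariance (ANCOVA) model". On missing data it says "Missing values will not be imputed". The code in SAP Appendix 1 has the line "model change = treatment region age etiology baseline_covariate", with no visit term, no repeated-measures statement and no LT 17 term.

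Protocol Table 6-1 schedules height and weight at LT 17, LT 18 and LT 19 and places consent at LT 17. Its footnote 1 says LT "17 should occur on the same day as CSPP100A2365E1" end of study. Protocol 9.4.3, headed "Handling of missing values/censoring/discontinuations", plans nothing. The SAP adds one sensitivity analysis in 1.2.6.1, which fills a missing LT 18 value with the LT 17 value.

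**The concern.** The population named for the endpoint and the population that reaches the model are not the same. PROC MIXED drops a record with a missing response. An enrolled patient without an LT 18 value therefore contributes nothing to the primary estimate, and that includes a secondary-hypertension patient who misses LT 18 but attends LT 19. LT 17 change should be highly predictive of LT 18 change, because the second contains the first.

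Loss is a realistic prospect. Table 6-1 has no visit between week 52 and week 104, study drug has stopped, Protocol 5.5.9 anticipates loss to follow-up, and withdrawals are not replaced. The comparison is about growth safety in children. An estimate that is less precise than it could be, or that is pulled toward zero by selective loss, could understate a real regimen difference.

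**Working it through.** **What the documents supply.** They give the two-sided 0.05 level, the endpoint, the EFS definition, the ANCOVA terms and the visit schedule. They give no sample size, SD, correlation, dropout rate or effect size (Protocol 9.6, SAP 1.3), so there is no planned figure to reproduce. Every numerical input below is an assumption.

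**Precision when loss is random.** Let p be the fraction missing at LT 18 and r the correlation of LT 17 and LT 18 change given the covariates. Relative to complete data, the variance is 1/(1−p) for complete cases and (1−r²)/(1−p) + r² when LT 17 is modelled. The ratio of interval widths is the square root of the ratio of these two. With r = 0.8:

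- p = 0.1: √(1.111/1.040) = 1.034
- p = 0.2: √(1.250/1.090) = 1.071
- p = 0.3: √(1.429/1.154) = 1.112

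Over r from 0.7 to 0.9 and p from 0.1 to 0.3, the excess width runs from about 2.5% to 15%.

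**Bias when loss is not random.** This was simulated with 4,000 per arm and 120 replicates (Monte Carlo error about 0.015 to 0.02 kg). Change to LT 17 had mean 5 kg and SD 5. Gain from LT 17 to LT 18 had mean 4 kg and SD 4. The correlation of the two gains was 0.3, so LT 18 change has SD √(25 + 16 + 12) = 7.3 kg and correlation 31/(5 × 7.3) = 0.85 with LT 17 change. Where loss depended on growth, the log-odds slope was 0.8 per SD of LT 17 change. Unequal rates were a log-odds shift of 0.7 in one arm. The fitted models had regimen and baseline weight only. Entries are bias in the regimen difference (kg) at reference dropout of 10% / 20% / 30%.

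| Scenario | Complete-case ANCOVA | LOCF from LT 17 |
|---|---|---|
| A. No effect; same dependence and rate in both arms | 0.01 / 0.02 / 0.00 | 0.01 / 0.02 / 0.01 |
| B. True −2 kg at LT 17 that persists; same dependence | +0.12 / +0.20 / +0.24 | +0.13 / +0.21 / +0.25 |
| C. No effect; dependence in one arm only | −0.56 / −1.00 / −1.43 | −0.19 / −0.26 / −0.27 |
| D. No effect; opposite dependence by arm | −1.13 / −2.02 / −2.84 | −0.19 / −0.31 / −0.37 |
| E. True −2 kg; dependence in one arm only | −0.43 / −0.82 / −1.17 | −0.05 / −0.05 / −0.02 |
| F. No effect; loss unrelated to growth, more in one arm | 0.00 / 0.00 / −0.01 | −0.33 / −0.53 / −0.66 |
| G. No effect; same dependence, unequal rates | −0.37 / −0.53 / −0.60 | −0.39 / −0.55 / −0.60 |

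An estimator that regresses on LT 17 within arm stayed within 0.02 kg throughout. That is expected, because dropout was generated to depend only on observed LT 17 growth.

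**Why LOCF does not settle it.** Carrying LT 17 forward sets the last year's gain to zero. In F the missing fractions at 20% reference dropout were 33% and 20%, so LOCF should be off by about (0.33 − 0.20) × 4 kg = 0.52 kg, which matches the table. LOCF reduces the bias in C, D and E, leaves it in B and G, and creates it in F. Agreement or disagreement with the primary result would therefore be hard to read.

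**Scale.** With an assumed 70 per arm and SD 7.3 kg, the standard error at 10/20/30% missing is 7.3 × √(2/(70(1−p))) = 1.3/1.4/1.5 kg. Scenario C is then about 0.4/0.7/1.0 standard errors and scenario D about 0.9/1.5/1.9.

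**Which repeated-measures model.** Growth accumulates, so the age-stratum effect on change should be larger at LT 18 than at LT 17. Height was simulated with 6 cm a year in the younger stratum, 2 cm in the older, and no regimen effect. With 30% loss among older patients of one arm and 10% elsewhere, a model sharing one age effect across visits was biased by about 0.25 cm. With 30% loss in opposite age strata by arm, the bias was about 0.5 cm. The planned ANCOVA had none in either case, and adding age-by-visit brought the repeated-measures bias back to about 0.01 cm.

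**The case against.** A reader might infer that the primary difference is biased whenever leaving depends on earlier growth. It is not. In scenario A the selection cancels: the mean change within each arm is distorted, but the difference and the test are not. A difference between regimens in the dependence, the dropout rate or LT 17 growth is also needed, and no passage shows that one exists.

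A reader might also take Protocol 9.4.3 to mean that missing LT 18 values are ignored altogether. The SAP's LOCF analysis does address them and does use LT 17. Its weakness is the assumption of a year without growth.

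Three further objections stand:

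- The sizes are illustrative. The large biases need opposite dependence in the two regimens, which nothing in the documents suggests. Under the assumed numbers, one-arm dependence costs about one standard error at most.
- The EFS is defined by signed consent, and the footnote says only that LT 17 should coincide with the final visit of the preceding study. LT 17 data are scheduled for all enrolled patients but not guaranteed.
- Protocol 9.4.2 itself specifies the ANCOVA, so replacing it is more than an edit to the SAP.

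A carelessly specified repeated-measures model could also do worse than the planned ANCOVA, as the height check shows.

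**Conclusion.** The point holds in a limited form. The primary ANCOVA is complete-case at LT 18 and leaves out a scheduled, strongly predictive measurement. The loss of precision applies even when dropout is random: about 3% to 11% in interval width at r = 0.8 and 10% to 30% missing. Bias is conditional. It arises when leaving depends on LT 17 growth and that dependence, the dropout rate or LT 17 growth differs by regimen. The direction of most concern is scenario B, where a true 2 kg deficit is pulled toward zero by 0.12 to 0.24 kg. The planned LOCF analysis would not reliably reveal or correct any of this. All sizes rest on assumed SDs, correlations, dropout rates and, for the standard errors, arm sizes. The documents do not allow the actual bias to be calculated, nor do they show that it is present. The improvement is worth making because it needs no new data.

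**What to change.** In SAP 1.2.6.1 and Appendix 1, specify a repeated-measures PROC MIXED model for change from baseline at LT 17 and LT 18, fitted to all EFS patients with an unstructured covariance within patient. Interact regimen, the baseline value of the variable analysed, region, age stratum and etiology all with visit, and report the aliskiren-minus-enalapril contrast at LT 18 with its 95% confidence interval. With complete data and full interaction, the LT 18 point estimate equals that of the planned ANCOVA, so the target is unchanged. In the secondary-hypertension end-of-study analysis, add LT 19 as a third visit.

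There are two acceptable placements:

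- Make this model the primary estimator, document the departure from Protocol 9.4.2 and keep the ANCOVA as supportive.
- Keep the ANCOVA as primary and make this model the main missing-data analysis in place of LOCF.

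In either case, report LT 18 missingness by regimen.

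The cost is SAP text, a few lines of code and, for the first placement, a documented change from the protocol. The model adds a few parameters and relies on data being missing at random given LT 17. It does not deal with loss that depends on unobserved growth after LT 17.
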